### Survey of Child Rearing Practices

Two focus groups with approximately six mothers of children under 5 years of age will be held in 3 control villages and 3 intervention villages. Mothers of malnourished children attending the feeding centers will not be involved.

Each focus group will have a leader and a recorder. The leaders will be [name], [name] and the senior psychologist. Information will be sought on all activities mothers do with their babies, their attitude towards play and child development, knowledge of child development and any games, songs and nursery rhymes, their aspirations for their children and who makes decisions in the family about child care and education.

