## Treatment Trial

### Samples

The study will be conducted in BINP nutrition centers in the Narsingdi Thana. Narsingdi which is situated near Dhaka and has a total population of 353,275 out of whom, there are 21,090 children below the age of 2 years. About 2229 of these children require nutritional supplementation and are enrolled in the BINP community nutrition centers. Narsingdi thana comprises 14 unions with 17-29 feeding centers in each union making a total of 326 feeding centers. Only six of these unions are accessible to Dhaka. For ethical reasons randomization into intervention and control will be by centers and not within each center. Twenty feeding centers from the two unions most accessible to Dhaka, will be selected to participate in the study. Only centers expected to enrol at least 10 children in the five month enrolment period will be selected. The sampling will be in two steps. In the first step, centers that are so close to each other that there is a high probability of the mothers or staff mixing socially, will be formed into clusters. One center from each cluster will then be randomly selected for further sampling. The first stage should prevent any spill over between treatment groups. In the second step 10 centers will be randomly selected for the intervention group and 10 for the control group, from the two unions.

A sample of 84 in each group will be sufficient to detect a difference of 6 developmental quotient (DQ) points between the groups with a power of 90% at the 5% level of significance. Assuming a loss of 16% we need 100 children in each group.

The study will have 3 groups making a total of 300 children who will have all measurements. However, because we want to assess the feasibility of incorporating this programme into a service model we will enrol into the intervention all children who present at the centers and fit the enrolment criteria during the enrolment period. The extra children will not have the measurements but enrolling all available children into the intervention will enable us to determine any problem with implementation at a service level.

**Treatment group:** The first 10 children referred to each intervention feeding center after the beginning of the study, and fulfil the selection criteria will be enrolled making a total of 100. However, all the children attending the intervention centers will have play opportunities.

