**Control group:** The first 10 children referred to each control feeding center after the beginning of the study and fulfil the selection criteria will be enrolled making a total of 100.

**Inclusion criteria:** weights for age  $<-2sd$ , aged between 6 and 24 months, mothers agree to participate in the study and intend to stay in the area for the next year.

**Exclusion criteria:** twins and disabled children will be included in the intervention for ethical and demonstration purposes but will not be part of the evaluated sample.

**Comparison group:** The child living nearest to every treated malnourished child with weight for age  $>-1sd$ , of the same age ( $\pm$  one month) and sex, maternal education and standard of housing will be enrolled making a total of 100.

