## Intervention

The intervention will be based on one used previously in Jamaica. It will be modified for Bangladesh following an initial rapid survey of child rearing practices. The mothers will meet in groups at the feeding center for one hour every week for a year. During the initial days, when mothers come daily to the centers, the play leaders will take the opportunity to work individually with mothers and children whenever possible. If the children are judged to be recovered and discharged from the usual services before the end of the year, they will still be included in the stimulation intervention. Those who do not attend will be visited at home and encouraged to come. At the meetings the mothers will be helped to make home made toys and they will be shown how to interact with their children and teach them simple concepts in such a way to improve their development. Only participatory methods or demonstrations will be used. Attention will be paid to improving the maternal child verbal interaction and to improving the mother's self esteem, child rearing and feeding practices. Records will be kept for each child of all contacts with the program staff.

**Training:** A short training workshop will be held to inform and motivate senior staff concerning the program. A two-week workshop will be held for the play leaders who will be running the program

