## Ethical Assurance for Protection of Human Rights

Describe in the space provided the justifications for conducting this research in human subjects. If the study needs observations on sick individuals, provide sufficient reasons for using them. Indicate how subject's rights are protected and if there is any benefit or risk to each subject of the study.

Signed informed consent of the parents will be obtained after thorough explanation of the purpose of the study, requirements of participation, and the benefits to the child. Another person will be acting as witness.

The study does not include any invasive procedure. However since the study subjects are malnourished children and are always at risk of acquiring illnesses, they will be examined by the study physicians upon enrolment. During the study minor illnesses will be treated and for any major illness, they will be referred to health centers. Liaison with the nearby health centers will be established and maintained to facilitate the referral.

Some of the information collected may be considered sensitive in nature. Therefore, measures will be taken to ensure strict confidentiality of the information obtained.

Approval will be sought from the Ethical Review Committee of ICDDR,B.

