### **Personnel**

PI and Co-PI will supervise the overall activities of the project. They will play the leading role in implementing the research in the field, they will pilot and train the appropriate personnel in all measurements, plan data entry, conduct analyses and write reports.

Co-PI is working at another institution and will give 35% of his time for this project.

The two psychologists will test 300 children and interview the mothers at the beginning and end of the study.

For the intervention group, we need one play leader at each intervention center making a total of 10.

For the control group health workers will arrange for the testing of the children and keep trace of their whereabouts. Therefore, one health worker can cover 2-3 feeding centers making a total of 4 health workers.

To make frequent visits to the project sites, which are situated outside the city in the rural area, we require a vehicle and a driver.

To supervise the work of the play leaders and help in record keeping, we need a research assistant.

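### Entry rests on the mother's agreement, sought after her center is allocated and covering different demands in each arm, so unrecorded selective refusal can unbalance the two malnourished groups

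*Protocol*

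**What the plan says.** All section names below are those of the psychosocial stimulation protocol; the file also holds an unrelated protocol with the same headings.

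- **Unit of allocation (Samples):** "For ethical reasons randomization into intervention and control will be by centers and not within each center". The allocation itself is described as "In the second step 10 centers will be randomly selected for the intervention group and 10 for the control group, from the two unions".
- **Timing of allocation:** the rapid survey comes before the main study (Study Design), yet its focus groups "will be held in 3 control villages and 3 intervention villages" (Survey of Child Rearing Practices). The Time Schedule places play-leader training in the block before enrolment.
- **Identification of children (Samples):** the evaluated intervention children are "The first 10 children referred to each intervention feeding center after the beginning of the study" who meet the criteria. The control rule is the same.
- **Entry criterion resting on the mother (Inclusion criteria):** "mothers agree to participate in the study and intend to stay in the area for the next year".
- **What participation involves in intervention centers (Intervention):** "The mothers will meet in groups at the feeding center for one hour every week for a year". Those who stay away are visited at home and encouraged to come.
- **What it involves in control centers:** the developmental tests, three-monthly anthropometry and a home visit (Measurements), and interviews at start and end. Budget Justifications (Personnel) adds: "For the control group health workers will arrange for the testing of the children and keep trace of their whereabouts". The abstract for the ethics committee promises controls the program once data collection is over.
- **Blinding (Measurements):** promised for the psychologists who test the children, and for no one else.

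**The concern.** Randomizing centers gives comparable groups of children only if the children evaluated are chosen in the same way in both arms. Here the last step of selection is the mother's own decision, and she decides when her center's arm is already fixed. Consent explains what participation requires and how the child benefits (Ethical Assurance), and both differ by arm. The protocol does not separate agreeing to be assessed from agreeing to join the program.

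A mother who declines fails a selection criterion, so her child is not among the 10 and the next eligible referral takes the place. The final 100 per group looks complete either way. If those who decline are the less motivated mothers, and they decline more often in one arm, the groups differ at the outset in something plausibly related to child development and to the maternal outcomes. No later analysis can recover mothers who were never recorded.

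**Working it through.** **1. Order of events.** Villages are already labelled control or intervention in a survey that precedes the main study, and play leaders, one per intervention center, are trained before enrolment opens. Children are then taken from referrals made after the study begins. Allocation therefore precedes identification and consent. This follows from several sections together, not from one explicit sentence.

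**2. The plan's own sample size.** Inputs from Samples: 84 per group, a 6-point difference, 90% power, 5% level, 16% loss. Inflation: 84/(1 − 0.16) = 100, as stated. The SD and sidedness are not stated. Solving the two-sample formula with a two-sided test:

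SD = 6 / [(1.96 + 1.2816) × √(2/84)] = 12.0

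(A one-sided test would imply 13.3.) I use 12 below.

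**3. Possible size of the shift.** The protocol gives no refusal rate, so two simple models show a range. Every refusal rate, correlation and DQ gap is an assumption.

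*Model A, sharp selection in one arm.* The least motivated fraction p of mothers decline in one arm and none do in the other. Mean motivation in the first arm rises by φ(z_p)/(1 − p) SD. Multiply by an assumed motivation–DQ correlation of 0.2 to 0.3 and by 12:

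| p | rise in motivation (SD) | shift in DQ points |
|---|---|---|
| 0.1 | 0.195 | 0.47 to 0.70 |
| 0.2 | 0.350 | 0.84 to 1.26 |
| 0.3 | 0.497 | 1.19 to 1.79 |

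*Model B, softer selection.* Half of mothers are highly motivated and consent at 95% in both arms. The rest consent at 95% in one arm and at a rate c in the other. The motivated share in that other arm is 0.95/(0.95 + c), against 0.50. For c = 0.9 it is 0.514; for c = 0.5 it is 0.655. The shares thus differ by 1.4 to 15.5 percentage points. With a DQ gap of 4 to 8 points between the two kinds of mother, the contrast moves by about 0.05 to 1.2 points.

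In either model, exchanging the arms reverses the sign.

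**4. Effect on the test.** With no true effect, SD 12 and 84 per group, the standard error is 12 × √(2/84) = 1.85.

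| shift | two-sided error rate, no clustering | with ICC 0.05, 8.4 children per center |
|---|---|---|
| 1 point | 8.4% | 7.5% |
| 2 points | 19.1% | 15.2% |

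The second column uses an assumed ICC and design effect 1 + 7.4 × 0.05 = 1.37.

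**5. Would the baseline comparison show it?** With 100 per group and SD 12, a baseline DQ difference reaches p < 0.05 only at about 1.96 × 12 × √(2/100) = 3.3 points, before any allowance for clustering. An imbalance of 1 to 2 points would usually pass unnoticed.

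**The case against.** Much can be said for the protocol. Both arms use one set of criteria and the same first-10 rule, and the weight and age limits leave little discretion. Baseline Bayley scores, home stimulation, socio-economic background and maternal knowledge are all measured; these are plausible correlates of motivation, initial differences will be examined, and covariate adjustment may be set out in an analysis plan. Nothing makes attendance a condition of being evaluated. Two-step consent would not conceal the arm. All of this stands, and it limits the problem. It does not remove it: the first-10 rule restrains staff, not mothers, and motivation itself is not measured.

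Some stronger readings are tempting, but the documents do not support them:

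- **That arm-specific staff recruit, or apply the twin and disability exclusions.** Play leaders run the program, and health workers arrange testing and trace children. No section says who screens or takes consent. The only relevant statement is that children "they will be examined by the study physicians upon enrolment", with no distinction by arm.
- **That a disability noticed during weekly contact could lead to later removal.** The exclusions are listed with the entry criteria, and no removal after enrolment is described.
- **That controls face testing only.** They also have repeated anthropometry, a home visit and interviews, with the program to follow. The difference in demands is real but narrower.
- **That the bias must favour the intervention.** The weekly hour may deter less motivated mothers there. Equally, immediate benefit may attract them, while control mothers asked to attend testing in Narsingdi town with benefit deferred may be the ones who decline.

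**Conclusion.** The point holds as a risk of recruitment bias in a cluster-randomized trial. Allocation comes first, entry depends on the mother's agreement, and that agreement carries a year of weekly sessions in one arm only. The two malnourished groups can therefore differ in maternal motivation before treatment.

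The direction is not determined; a shift in favour of the intervention is plausible because of the weekly burden. The size is unknown. Under the assumptions above it runs from near zero to about 1 to 2 DQ points. The top of that range, 1.79 points or about 30% of the 6-point target (1.79/6), requires 30% refusal confined to one arm and perfectly ordered by motivation, so it is an upper illustration and not an estimate. If refusals are rare the bias is small, but the protocol gives no expected rate and describes no means of learning it. The consent forms are not part of the text examined, so nothing here rests on their wording. The change is worth making because it is cheap and the lost information cannot be recovered later.

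**What to change.** 1. Replace the agreement part of the inclusion criterion with the mother's agreement to the assessments. Use the same wording in all 20 centers and ask before the invitation to the play sessions. The intention-to-stay criterion can remain.
2. Define the evaluated sample in each center as the first 10 consecutive eligible referrals by register date whose mothers agree to the assessments, and evaluate them whether or not the mother attends sessions.
3. Log eligible, approached and refusing mothers by center and arm, and report the counts.

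This fits the existing design, which already separates receiving the program from being measured: eligible children beyond the first 10 in intervention centers join without the measurements.

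The cost is a reworded criterion, a two-step consent and a short log, with no extra staff or visits. The downside is that some evaluated intervention mothers will attend little, so the estimate becomes the effect of offering the program. That matches the stated aim of extending it to all centers. The allocation remains unconcealed, so the change reduces the risk and makes it visible, but does not abolish it.

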## Measurements

The Drs [name] and [name] will do the piloting and quality control of all measurements.

**Developmental level:** The infants will be assessed on the Bayley Scales of Mental Development at the beginning and end of the study. We have used these scales before in Bangladesh and good interobserver reliability was attained. The assessments will be done by one of two trained female psychologists who are unaware of the children's group assignment. Care will be taken to keep the testers blind to the child's group and the testing will not be done in the feeding centers.

**Behavior:** The children's behavior during the tests will be rated by the testers on five 9 point scales: the amount of vocalisation, co-operation with the test procedure, activity level, emotional tone and response to examiner. These scales have also been used before in Bangladesh and are modified from those of Bayley and Wolke et alxxi.

**Temperament:** At the end of the study the mothers will be given a questionnaire by the psychologists concerning their child's temperament. There is no standardised test for Bangladeshi children. We will therefore pilot an instrument developed by Mary Rothbartxxii and one being developed by Theodore Wachs from Purdue University for use in Jamaica and Peru and combine and modify the instruments where necessary. The following behaviors will be investigated: activity level, positive emotionality (smiling/laughing), negative emotionality (fussing/crying), social approach (response to strange adults), object fear (fear of new objects), attention/orientation, manageability (response to frustration/ co-operativeness), soothability (reduction of distress in response to soothing). These behaviors are well recognised components of temperamentxxiii.

**Anthropometry:** All children will have their weights, lengths, head and mid upper arm circumferences measured using standard techniques on enrolment and every 3 months by the research assistant.

**Socio-economic background and stimulation in the home:** All homes will be visited at the beginning of the study and information will be sought on the families' wealth, standard of housing, family structure and parental characteristics. The stimulation in the home will be assessed using a modified version of the Betty Caldwell home inventoryxxiv, which was modified for Bangladesh in a previous study by this research group.

**Child rearing practices:** The mothers' knowledge of child development and child rearing practices will be assessed at the beginning and end of the study by the psychologist.

**Hb Measurement:** As suggested by one of the reviewers, we will consider testing the children for their Hb level provided funds are available.

**Quality Control of Measurements:** Before the study begins, and after training the measurers, inter-observer reliabilities will be assessed for all measures. Values of over  $r > 0.9$  are expected for all measures and training will continue until this standard is attained. Five to 10 percent of all tests throughout the study will be observed and independently scored by an observer. Test-re-test reliabilities

Principal Investigator: Last, first, middle [name]

will also be assessed at the beginning of the study for the temperament scales and Bayley test in 20 subjects and values  $>0.7$  are expected.

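### Tester training ends at inter-observer r > 0.9, which, read as a correlation, cannot detect a constant scoring difference between the two psychologists

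*Protocol*

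**What the plan says.** All references are to the psychosocial stimulation proposal in the protocol file.

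- **Who tests (Measurements, Developmental level).** "The assessments will be done by one of two trained female psychologists who are unaware of the children's group assignment". The same testers rate behavior on five 9-point scales.
- **Sign-off (Measurements, Quality Control of Measurements).** Before the study, "inter-observer reliabilities will be assessed for all measures". Values above r > 0.9 "are expected for all measures and training will continue until this standard is attained". The type of coefficient is not given.
- **During the study (same paragraph).** Five to ten percent "of all tests throughout the study will be observed and independently scored by an observer". No statistic, limit or action is attached. Test-retest values above 0.7 are expected for the Bayley test and the temperament scales in 20 subjects, again without a limit on a difference in means.
- **Size of effect sought (Samples).** The figure of 84 evaluable children per arm is set to find a "difference of 6 developmental quotient (DQ) points between the groups with a power of 90% at the 5% level of significance". The SD is not stated.
- **Analysis (Data Analysis).** The multilevel model has the child, the feeding center and the treatment group as its levels. Tester is not mentioned.

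**The concern.** When two people's scores are pooled into arm means, they must agree in level as well as in rank order. A correlation measures only the second. If one psychologist credits items more generously and scores every child several points higher, r between the two is exactly what it would have been without that habit. Training would be declared complete.

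At stake is the comparison of mean DQ between arms. A persistent offset adds variance to the scores, and to before-after change when a child meets a different tester at the end. If the two testers see different proportions of each arm, part of the offset passes into the treatment contrast. The sign-off rule acts before any data are analyzed, so an analysis plan cannot repair it later.

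**Working it through.** **Inputs from the protocol.** 84 evaluable per group, 6 points, 90% power, 5% level, 16% loss, pass mark r > 0.9, two testers, 300 children tested at the beginning and end.

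**Assumptions.** Two-sided test; r > 0.9 read as a Pearson correlation; constant offset d between testers; true r of 0.91 to 0.98. The offset is illustrative: the protocol gives no estimate of one.

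**1. The plan's own figure, and the SD behind it.** n = 2(1.96 + 1.2816)² SD² / 6². Setting n = 84 gives SD² = 84 × 36 / (2 × 10.51) = 143.9, so SD = 12.0. Put back, SD 12 gives n = 84.06 and power 0.900 at 84 per group. The enrolment figure follows: 84 / 0.84 = 100. Because the SD is inferred, 10 to 15 is used as a range.

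**2. What an offset does to each statistic.** Pearson r: no change for any d. For two raters with equal variance, large-sample absolute agreement is

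ICC = r·SD² / (SD² + d²/2).

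With SD 12, r = 0.95, d = 6: subject variance 136.8, error 7.2, rater term 18, so ICC = 136.8 / 162 = 0.844. At d = 6 over the range:

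| SD | r = 0.91 | r = 0.95 | r = 0.98 |
|---|---|---|---|
| 10 | 0.77 | 0.81 | 0.83 |
| 12 | 0.81 | 0.84 | 0.87 |
| 15 | 0.84 | 0.88 | 0.91 |

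r passes 0.9 in every cell. The ICC passes only in the last (0.907).

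**3. As a pass rule.** In simulation with 20 paired tests (an assumed number), SD 12 and true r = 0.95, the rule r > 0.9 is met about 95% of the time with or without a 6-point offset. The rule ICC > 0.9 is met 94% of the time without the offset and 8% with it.

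**4. What ICC > 0.9 alone would still allow.** Solving for d: d² = 2·SD²(r/0.9 − 1). With SD 12 and r = 0.95, d² = 288 × 0.0556 = 16, so d = 4 points. With r = 0.98 it is about 5 (d² = 25.6). The ICC therefore needs a separate limit on the mean difference.

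**5. Effect on the trial.** Let one tester see a share p1 of the intervention arm and p0 of the control arm. Bias = d(p1 − p0), and the within-arm variance is about 144 + d²p(1 − p). With d = 6, 84 per arm, no clustering and no tester term:

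| Shares | Bias (points) | Consequence |
|---|---|---|
| 50:50 in both arms | 0 | SD = √(144 + 9) = 12.37; power 88% |
| 60:40 v 40:60 | 1.2 | type I error about 10% |
| 70:30 v 30:70 | 2.4 | type I error about 24% |

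**6. How likely unequal shares are.** If tester is random child by child, the difference in shares has SD √(2 × 0.25/84) = 0.077. A 20-point gap is then 2.6 SDs, about 1%. If whole centers go to one tester at random, the SD is √(2 × 0.25/10) = 0.22 and a gap of at least 20 points occurs about half the time. The protocol does not say how children are booked.

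**The case against.** The strongest reply is that harm to the treatment contrast is conditional. The testers are blind to group. Testing takes place in one rented house in Narsingdi town, not at the centers, and nothing ties either psychologist to an arm or a center. Two investigators oversee quality control, and the scales have been used in Bangladesh before with good inter-observer reliability. With balanced testers the cost is about two percentage points of power. All of this stands and limits the size of the point. None of it ensures balance, and none of it lets r detect a difference in level.

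It is also fair that r is not named as Pearson's. An absolute-agreement coefficient may have been meant, but the text does not say so, and a consistency-type ICC would share the blindness. A tester term and appointment booking can properly be left to an analysis plan or field manual, so their absence is not the defect here.

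Two stronger readings are tempting and unsupported:

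- A reader might infer that the ongoing checks also rest on r > 0.9. The protocol attaches that mark only to the assessment before the study. The double-scored tests have no statistic at all, and their data could reveal an offset if means were compared.
- A reader might infer that an offset equal to the target would shift the estimated effect by 6 points. That requires one tester per arm, which nothing in the protocol suggests.

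**Conclusion.** The point holds in a limited form. As written, the rule that ends training cannot see a constant difference between the psychologists, and no other stated check sets a limit on one. This is certain if r is a correlation, its usual meaning.

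The size of the consequence is not certain. An offset of 6 points is a hypothetical value chosen for scale against the target effect. The SD of 12 is inferred, and the tester shares are unknown. Under those assumptions the cost runs from a small loss of power (90% to about 88%) with equal shares to 1.2 points of bias, 20% of the target, at 60:40 versus 40:60. The calculation ignores clustering and assumes no tester adjustment. The protocol's text does not show that the arm comparison will be biased. The case for change is that a better rule is available at little cost from double scoring that is already planned.

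**What to change.** 1. **Sign-off and ongoing double scoring.** Replace r > 0.9 by an absolute-agreement ICC above 0.9 together with a stated limit on the mean difference between the two psychologists, for example 2 DQ points on the Bayley, with retraining if either fails. Apply both before the study and to the double-scored tests, and set corresponding limits for the behavior ratings in their own units. State that the double scoring pairs the two psychologists, or pairs each with the same observer, so that their difference can be estimated.

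   A 2-point limit is workable. With SD 12 and r = 0.95, paired differences have SD √(2 × 7.2) = 3.8. Five to ten percent of about 600 tests (300 children tested twice, before losses) is 30 to 60 pairs. If these pair the two psychologists, the standard error is 0.7 to 0.5 points. At 2 points the bias under 60:40 versus 40:60 would be 0.2 × 2 = 0.4 points.

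2. **Analysis.** Record who tested each child at each visit and include tester as a fixed factor in the multilevel model.

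3. **Booking.** Where practical, split each center's children between the two psychologists.

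The cost is a change of wording, a different statistic on data already planned, one model term and a minor scheduling constraint across the centers.
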